### 4.1.1 MMRM assuming a log-normal distribution

An MMRM will be fitted on log-transformed change from baseline. Log-transformed change from baseline is calculated as the visit value in natural logarithm minus the baseline value in natural logarithm.

The visit statistically tested within the MMRM model is week 12 (day 85). All previous available data on scheduled visits will be used in the model. Fixed factors of the model will be treatment, visit and treatment\*visit interaction. The natural log-transformed baseline value of the outcome variable will be used as a covariate. Visits within subjects will be considered as repeated measurements.

Comparisons derived from the model will be:

- AZD8233 **CCI** versus placebo,
- AZD8233 **CCI** versus placebo
- AZD8233 **CCI** versus placebo
- AZD8233 **CCI** versus AZD8233 **CCI**
- AZD8233 **CCI** versus AZD8233 **CCI**
- AZD8233 **CCI** versus AZD8233 **CCI**

The REML approach will be used for the estimation of the variance and covariance parameters of the linear mixed model; two-sided difference test, with alpha level at 5% will be used for the comparisons and for the t-type confidence interval calculation.

The model will be fitted with an unstructured covariance structure and the Kenward-Roger correction applied to obtain the degrees of freedom.

In case the model will not converge for any reason, the following hierarchical model fitting procedure will be adopted:

1. The MMRM will be fitted using a SP(POW) covariance structure; Visit will be expressed as scheduled visit days to accomplish the variance-covariance matrix estimation.
2. The MMRM will be fitted using a CS covariance structure
3. An ANCOVA model will be used

The reportable results from the model will be:

- The LSmean and their 95% CI for each group for the log-transformed change from baseline
- Back transformed LSmean for each group, which correspond to the estimated relative change from baseline; back transformed LSmean is derived as  $[\text{EXP}(\text{LSmean})]$ .
- 95% CI of the back transformed LSmean for each group; 95% CI of the back transformed LSmeans is derived as  $[\text{EXP}(\text{lower limit of the 95\% CI of the LSmean})]$ ;  $[\text{EXP}(\text{upper limit of the 95\% CI of the LSmean})]$ .
- The geometric mean ratio between active groups and the control group; the ratio is calculated as  $\text{EXP}(\text{of the LSmean of the difference})$
- The 95% CI of the geometric mean ratio; the 95% CI of the ratio is calculated as  $[\text{EXP}(\text{Lower limit of the 95\% CI of the LSmean of the difference})]$ ;  $[\text{EXP}(\text{Upper limit of the 95\% CI of the LSmean of the difference})]$ .
- P-value of the geometric mean ratio

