## 6.3 Measures to Minimise Bias: Randomization and Blinding

All participants will be centrally assigned to randomized study intervention using a RTSM

system. Before the study is initiated, the telephone number and call-in directions and/or the log in information & directions for the RTSM will be provided to each site.

To simplify supply of study drug, randomization will be stratified based on the region in which the site is located. This will achieve greater balance within each region compared to simple randomization. Currently, two regions are planned: Europe and North America.

Study intervention will be dispensed at the study visits summarized in SoA.

The RTSM will provide to the Investigator(s) or pharmacists the kit identification number to be allocated to the participant at the dispensing visit. Routines for this will be described in the RTSM user manual that will be provided to each centre.

The randomisation code should not be broken except in medical emergencies when the appropriate management of the participant requires knowledge of the treatment randomisation. The Investigator documents and reports the action to AstraZeneca, without revealing the treatment given to participant to the AstraZeneca staff. AstraZeneca retains the right to break the code for SAEs that are unexpected and are suspected to be causally related to an investigational product and that potentially require expedited reporting to regulatory authorities. Randomisation codes will not be broken for the planned analyses of data until all decisions on the evaluability of the data from each individual participant have been made and documented.

The RTSM will be programmed with blind-breaking instructions. In case of an emergency, in which the knowledge of the specific blinded study treatment will affect the immediate management of the participant's condition (eg, antidote available), the Investigator has the sole responsibility for determining if unblinding of a participants' intervention assignment is warranted. Participant safety must always be the first consideration in making such a determination. If a participant's intervention assignment is unblinded, the sponsor must be notified within 24 hours after breaking the blind. The Investigator documents and reports the action to AstraZeneca, without revealing the treatment given to participant to the AstraZeneca staff.

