### 9.2 Sample Size Determination

Approximately 108 participants will be randomly assigned to the four study arms so that at least 80 evaluable participants completed treatment up until and including visit 10 (week 12). Any participant who receives at least one dose of study intervention is considered evaluable and is included in the full analysis set. Participants are randomly assigned to study treatment cohorts in a ratio of 1:1:1:1.

The sample size of 20 participants per arm will provide 90% power in a two-sided t-test at 5% significance level to detect a difference of 0.33 on the log scale; 0.33 on the log scale is considered sufficient to distinguish the effect of the **CCI** dose from the effect of the **CCI** dose. The common SD for log-transformed LDL-C is assumed to be 0.3.

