#### **9.4.2 Efficacy**

The analysis and presentation of efficacy and exploratory endpoints will be based on participants in the full analysis set.

For selected efficacy variables, if not specified otherwise, a mixed model for repeated measures will be fit using log transformed data and results transformed back to geometric mean ratios for the purpose of presentation and interpretation. The mixed model for repeated measures will include the relevant log transformed baseline biomarker value as a covariate. Time point (visit number), treatment, and the interaction between time point and treatment will be included as factors. The response variable will be change from baseline in log transformed biomarker value. The model will be fit with an unstructured covariance structure, and the Kenward-Roger correction applied to obtain the degrees of freedom. Estimation of the treatment effect will be done for each visit after baseline. In case of issues when fitting the model to the data, a hierarchical model fitting procedure will be described in the statistical analysis plan.

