## 1.2 Study design

This is a randomized, parallel, double-blind, placebo-controlled, dose-ranging Phase 2b study in approximately 108 participants with dyslipidaemia. The study will be conducted in up to 25 sites in up to 4 countries.

The screening period starts up to 42 days before the randomization visit and ends on Day -1. Eligible participants will attend 7 visits during the treatment period and 7 additional visits during the safety follow up period. Eligible participants are randomized across four different treatment arms in a 1:1:1:1 ratio stratified by region (North America vs Europe) for a 12-week treatment period. The planned treatment arms are AZD8233 CCI SC, AZD8233 CCI SC, AZD8233 CCI SC, and Placebo SC on Days 1, 8, 29, and 57.

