#### **4.1.3 Sensitivity analysis 1**

The sensitivity analysis 1 will consist of repeating the MMRM assuming a log-normal distribution including only subjects who have completed the treatment period as per protocol and who have no relevant IPDs. Subjects who have completed the treatment period as per protocol are the subjects who reached week 12 and received all four scheduled doses of IP; subjects who received wrong dose of IP or wrong treatment will be excluded. Further, relevant IPDs are defined in section 2.2.

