#### **4.1.4 Sensitivity analysis 2**

The sensitivity analysis 2 will consist of repeating MMRM assuming a log-normal distribution (without any back-up strategy) using the pattern-mixture model with control-based pattern imputation ([reference 1](#)). To implement this approach, we firstly use MCMC to impute non monotone MAR missing data for subjects who have completed the treatment period as per protocol (reached week 12 and received all four doses of IP). Then we use the resulting dataset to sequentially impute missing data at each visit using a monotone regression approach. Sequential imputation will be done in two ways:

- considering only placebo group for the estimations of missing data for placebo patients and for active subjects at visits for which the previous scheduled dose of IP is missing or not as per protocol (wrong dose of IP or a wrong treatment);
- considering only the relevant active group for the estimations of missing data for active subjects at visits for which the previous scheduled dose of IP was taken as scheduled.

The results from each imputation set will be combined using Rubin's formulas

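### Randomisation is stratified by region but region is in neither MMRM; if region predicts LDL-C change, the tests are mildly conservative, and adding it costs one degree of freedom

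*SAP*

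**What the plan says.** Protocol 6.3 sets the stratification and gives its reason: "To simplify supply of study drug, randomization will be stratified based on the region in which the site is located". It names two planned regions, Europe and North America, and notes that arms will be better balanced within region than under simple randomisation. SAP 1.2 confirms the allocation as 1:1:1:1, "ratio stratified by region (North America vs Europe) for a 12-week treatment period".

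The analysis models do not use the stratum. SAP 4.1.1 (log scale, primary) starts its list with "Fixed factors of the model will be treatment, visit and" and completes it with the treatment-by-visit interaction; the log baseline value is the covariate. SAP 4.1.2 (percent change) has the same factors with the untransformed baseline. Protocol 9.4.2 agrees: "Time point (visit number), treatment, and the interaction between time point and treatment will be included as factors", plus log baseline. In the SAP's analysis methods, region appears only in the demographic and recruitment summaries.

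Both sensitivity analyses inherit the model. SAP 4.1.3 states "The sensitivity analysis 1 will consist of repeating the MMRM assuming a log-normal distribution" in a restricted set of subjects, and SAP 4.1.4 states "The sensitivity analysis 2 will consist of repeating MMRM assuming a log-normal distribution" after control-based imputation. Neither document says why region is left out.

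**The concern.** Stratifying by region keeps each arm's regional mix nearly the same, so differences between regions largely cancel from the treatment contrast. A model without region leaves those differences in the residual variance. The reported standard error is then larger than the true sampling SD of the estimate: the point estimate gains from the balance, but the interval and p-value do not show it.

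This study is meant to choose a dose, and its main test compares two active doses, so the width of the dose-versus-dose intervals at Week 12 matters. Because both sensitivity analyses repeat the same model, no planned analysis would show whether the omission makes a difference.

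**Working it through.** **Inputs from the documents.** Two-sided alpha 5%, difference 0.33 on the log scale, SD 0.3 ("The common SD for log-transformed LDL-C is assumed to be 0.3"), 20 per arm for 90% power (protocol 9.2, SAP 1.3). About 108 are randomised, so 108/4 = 27 per arm; at least 80 are to complete to Week 12, so 20 per arm.

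**Inputs assumed.** Region gap after baseline adjustment of 0.1, 0.2 or 0.3 ln units; regional split 50/50 or 70/30; residual SD within region 0.30 or 0.26; region balanced within each arm. The documents give none of these.

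**The plan's own figure.** A two-sample t-test with 20 per arm, difference 0.33 and SD 0.3 has 92.4% power; 19 per arm gives 91.0%. The stated 90% with 20 per arm is therefore met with a small margin.

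**Model.** A Week 12 ANCOVA with four arms and baseline stands in for the Week 12 contrast of the MMRM. The true SD of the contrast is σ√(2/n) = 0.30 × √(2/20) = 0.095.
- Without region, the residual sum of squares is σ² times a noncentral chi-square with 4n − 5 df and noncentrality λ = 4n·p(1 − p)·gap²/σ².
- With region, it is σ² times a central chi-square with 4n − 6 df.

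For n = 20, p = 0.5, σ = 0.30 and gap 0.1, λ = 80 × 0.25 × 0.01/0.09 = 2.22 on 75 df. The root-mean-square inflation is √(1 + 2.22/75) = 1.015. The mean standard error is 1.011 times the true SD, because a sample SD averages slightly below σ.

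**Results, 20 per arm, 50/50, σ = 0.30** (2,000,000 draws per cell):

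| Gap (ln) | λ | Mean SE / true SD | Alpha without region | Power without | Power with |
|---|---|---|---|---|---|
| 0.1 | 2.22 | 1.011 | 4.7% | 92.6% | 93.0% |
| 0.2 | 8.89 | 1.054 | 3.8% | 91.3% | 93.0% |
| 0.3 | 20.0 | 1.122 | 2.8% | 88.9% | 93.0% |

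With region in the model, alpha is 5.0% throughout.

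**Other settings, same three gaps.**
- σ = 0.26, 50/50, 20 per arm: SE ratio 1.016, 1.073, 1.160; alpha 4.6%, 3.5%, 2.3%.
- 70/30 split, σ 0.26–0.30: SE excess about 1%, 5–6%, 10–14%; alpha about 4.7%, 3.7–4.0%, 2.6–3.1%.
- 27 per arm, 50/50, σ = 0.30: power 97.8%, 97.3%, 96.4% without region against 98.0% with it, so the largest loss is 98.0 − 96.4 = 1.6 points.

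**Cross-checks.** Direct ANCOVA simulation (20,000 runs per cell, σ = 0.30, 20 per arm) gave mean standard errors of 0.0965, 0.1006 and 0.1071 without region against about 0.0952 with it, and an empirical SD of 0.095–0.097. A separate calculation by the share of residual variance due to region gave alpha 4.45%, 3.9% and 2.9% for shares of 5%, 10% and 20%. Simulation with assumed blocks of four within region agreed: 4.3–4.7%, 3.9–4.2% and 2.9%. With unstratified allocation and a 10% share, alpha was 4.8%, so the conservatism comes from stratifying and then not adjusting.

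**Cost of the extra term.** Residual df fall from 75 to 74 at N = 80 and from 103 to 102 at N = 108. The critical t rises by about 0.02% and 0.01%.

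**The case against.** The strongest objection concerns power. The planned SD of 0.3 is stated for a plain t-test, so it is most naturally read as already containing any between-region variance. The table holds 0.30 as the within-region SD and adds the region variance on top. With the total SD held at 0.30 instead (50/50, 20 per arm), power for gaps of 0.1, 0.2 and 0.3 is about 93%, 94% and 95% without region and about 94%, 95% and 98% with it. On that reading, power never falls below the planned 90%. This stands: the 88.9% figure should not be read as a missed power target. But region still raises power, and the alpha and standard-error mismatch remains on either reading.

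Second, the effect is hypothetical. The outcome is a baseline-adjusted change measured in a central laboratory, in participants on stable statin therapy, which makes a large residual gap less likely. A gap of 0.3 nearly equals the 0.33 design difference and is extreme. At 0.1 the loss is about 0.4 points of power at 20 per arm. That also stands, and it is why the point is minor.

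Third, region balance within arm is assumed. No block size is given, and dropout could disturb the balance, which would shrink the mismatch.

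Fourth, protocol and SAP prespecify the same model, the stratum was chosen for drug supply, and the error is on the safe side. All true, but the motive for stratifying does not alter its effect on the variance.

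**Conclusion.** The concern holds as a minor efficiency and calibration point. It is conditional on region predicting Week 12 change after baseline adjustment, and it does not threaten the study's validity. For moderate gaps of 0.1–0.2 ln units, with a 50/50 split and residual SD 0.26–0.30, the standard error is about 1–7% too large and actual alpha is about 3.5–4.7%. Only the extreme 0.3 gap goes further: 12–16% and 2.3–2.8%. The gaps, splits and within-arm balance are assumptions. Only the log-scale Week 12 LDL-C comparison was computed, in a single-visit form; the percent-change and PCSK9 models were not.

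**What to change.** Add region (Europe / North America) as a fixed factor in SAP 4.1.1 and 4.1.2, in the ANCOVA fallback of each, and in sensitivity analyses 1 and 2. The cost is one degree of freedom, one programming line and a short SAP wording change. That cost is for a main effect with the two planned regions. A region-by-visit term would need seven parameters over the seven post-baseline visits to Week 12 and is not part of this proposal. If the sponsor prefers to leave region out, the SAP should say why.

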#### 4.1.2 MMRM assuming a normal distribution

An MMRM will be fitted on percent change from baseline. Percent change from baseline is calculated as the visit value minus the baseline value divided by the baseline value \*100.

The visit statistically tested within the MMRM is week 12 (day 85). All previous available data on scheduled visits will be used in the model. Fixed factors of the model will be treatment, visit and treatment\*visit interaction. The baseline value of the outcome variable will be used as a covariate. Visits within subjects will be considered as repeated measurements.

Comparisons derived from the model will be:

- AZD8233 **CCI** versus placebo,
- AZD8233 **CCI** versus placebo
- AZD8233 **CCI** versus placebo
- AZD8233 **CCI** versus AZD8233 **CCI**
- AZD8233 **CCI** versus AZD8233 **CCI**
- AZD8233 **CCI** versus AZD8233 **CCI**

The REML approach will be used for the estimation of the variance and covariance parameters of the linear mixed model; two-sided difference test, with alpha level at 5% will be used for the comparisons and for the t-type confidence interval calculation.

The model will be fitted with an unstructured covariance structure and the Kenward-Roger correction applied to obtain the degrees of freedom.

In case the model will not converge for any reason, the following hierarchical model fitting procedure will be adopted:

1. The MMRM will be fitted using a SP(POW) covariance structure; Visit will be expressed as scheduled visit days to accomplish the variance-covariance matrix estimation.
2. The MMRM will be fitted using a CS covariance structure.
3. An ANCOVA model will be used.

The reportable results from the model will be:

- The LSmean and their 95% CI for each group for the percent change from baseline
- The LSmean of the difference between active groups and the control group
- The 95% CI of the LSmean of the difference
- P-value of the LSmean of the difference

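### Both MMRMs use one baseline slope for all seven visits although only Week 12 is tested; adding a baseline-by-visit term is a cheap improvement

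*SAP*

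**What the plan says.** Both mixed models in the SAP have treatment, visit and treatment-by-visit as fixed factors, with baseline entered once.

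- SAP 4.1.1 (log scale): "The natural log-transformed baseline value of the outcome variable will be used as a covariate".
- SAP 4.1.2 (percent change): "The baseline value of the outcome variable will be used as a covariate".
- Protocol 9.4.2 agrees: "The mixed model for repeated measures will include the relevant log transformed baseline biomarker value as a covariate". The only interaction it names is between time point and treatment.

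No baseline-by-visit term appears in either document. The models take all scheduled visits up to Week 12, which SAP Table 3 gives as Weeks 1, 3, 4, 6, 8, 10 and 12 (Days 8 to 85). Week 12 is the only visit tested. The covariance is unstructured with Kenward-Roger degrees of freedom.

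The log-scale model serves LDL-C and PCSK9, and sensitivity analyses 1 and 2 repeat it. The percent-change model serves LDL-C and the other lipids. The last convergence fallback is an ANCOVA for which no visit is stated; fitted at Week 12, it would have its own slope.

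**The concern.** The treatment effect may differ at each visit, but the dependence on baseline may not. There is little reason to expect that dependence to stay constant. The Day 8 sample is taken before the second injection, one week after a single dose. Day 85 follows four doses and, by Protocol 4.2, should be close to steady state.

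A common slope is a weighted average over visits, and it is then used to adjust the one visit that matters. If the Week 12 slope differs from that average, two things follow. Some of the precision that baseline adjustment should buy is lost. A chance baseline difference between arms of 20 to 27 is also corrected by the wrong amount. A third issue arises with missing data: if dropout depends on baseline, the mean model at Week 12 has to be right for the likelihood analysis to be unbiased.

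**Working it through.** **Inputs from the documents.** Protocol 9.2 on size: "The sample size of 20 participants per arm will provide 90% power in a two-sided t-test at 5% significance level". The target difference is 0.33 log units. On spread: "The common SD for log-transformed LDL-C is assumed to be 0.3". On allocation: "Participants are randomly assigned to study treatment cohorts in a ratio of 1:1:1:1". The plan randomizes 108 to have at least 80 complete Week 12, that is 27 and 20 per arm, an allowed loss of 28/108 = 26%. SAP 4.1.1: "two-sided difference test, with alpha level at 5% will be used for the comparisons".

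**Inputs assumed, because the documents do not give them.** Baseline log SD 0.25 (range 0.20-0.30). Slopes of change on baseline running from -0.1 at Week 1 to -0.4 at Week 12, or to -0.7 as an extreme. Residual SD either flat or rising from 0.20 to 0.30. Residual correlation compound-symmetric at 0.6, autoregressive at 0.6-0.8 per 28 days, or a mixture.

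**Step 1: the plan's own figure.** SE = 0.3 × √(2/20) = 0.0949, and 0.33/0.0949 = 3.48. Power is 92.4% by the t distribution and 93.6% by the normal. The smallest n for 90% is 19 (t) or 18 (normal). The stated 20 per arm holds and is slightly conservative.

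**Step 2: which visits set the slope.** With residual covariance S over the seven visits, the generalized least squares weights are w = S⁻¹1 / (1′S⁻¹1).

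- Flat SD: Weeks 1-4 carry 43-47% (they are 3 of 7 visits, or 43%); Week 12 alone carries 14-40%.
- Rising SD: Weeks 1-4 carry 68% to over 100%; Week 12 carries -10% to 16%.
- In every pattern, visits before Week 12 carry at least 60%.

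**Step 3: effect at Week 12.** Let the gap be the difference between the common slope and the Week 12 slope.

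- Variance factor = 1 + (baseline SD² × gap²) / (residual SD²) = 1 + 0.0625 × gap² / 0.09.
- Shift from a one-SE baseline imbalance at 27 per arm = gap × 0.25 × √(2/27) = gap × 0.068.

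The table uses the mixed correlation pattern. Power comes from 6,000 simulated complete-data trials per scenario at 20 per arm.

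| Slopes, residual SD | Common / Week 12 slope | Gap | Variance factor | SE | Shift | Power: common vs per-visit slope |
|---|---|---|---|---|---|---|
| -0.1 to -0.4, flat | -0.254 / -0.400 | 0.146 | 1.015 | +0.7% | 0.010 | 92.3% vs 92.4% |
| -0.1 to -0.4, rising | -0.150 / -0.400 | 0.250 | 1.043 | +2.1% | 0.017 | 91.8% vs 92.4% |
| -0.1 to -0.7, rising | -0.200 / -0.700 | 0.500 | 1.174 | +8.3% | 0.034 | 88.2% vs 92.4% |

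Over all the correlation patterns, the SE excess is about 1-3% for slopes to -0.4 and 3-11% for slopes to -0.7. In the simulations bias was at most 0.0015 and type I error was 4.4-5.6% under both models.

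**Step 4: cost of the extra term.** Fixed-effect parameters go from 4 × 7 + 1 = 29 to 4 × 7 + 7 = 35, against 80 × 7 = 560 or 108 × 7 = 756 observations. If all slopes are equal, Week 12 variance rises by about 1.3% (N = 80) or 1.0% (N = 108). Power falls from 92.98% to 92.66%, or from 97.95% to 97.85%, so by 0.1-0.3 points. Setting the variance lost equal to 1/(N-6) gives a break-even gap of 0.3 / (0.25 × √74) = 0.14 at N = 80. Over baseline SDs of 0.20-0.30 and both values of N, break-even runs from 0.10 to 0.17.

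**Step 5: dropout.** Large two-arm data sets were simulated with a true difference of -0.33, baseline SD 0.25, correlation 0.7 per 28 days and 21-25% dropout. Dropout depended only on baseline, in opposite directions in the two arms, which is deliberately adverse. The common-slope estimate lay closer to zero than the per-visit-slope estimate by 0.010-0.023 for slopes to -0.4, and by 0.020-0.046 for slopes to -0.7. The per-visit-slope model stayed within 0.004 of the truth. Without dropout the two models agreed.

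**The case against.** The strongest reply is that this is a modelling preference. The SAP model is the protocol's prespecified model, nothing contradicts it, and randomization protects the contrast. That stands: with complete data the common slope is valid, and in the moderate scenarios it costs at most 0.6 power points.

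The extra term is also not free. In the flat-SD scenario the gap of 0.146 barely exceeds the break-even value of 0.14, so gain and cost nearly cancel. Below break-even, the change makes Week 12 slightly less precise. This stands too, and the cost belongs beside the benefit.

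A reader might infer that the earliest visits, being least variable, dominate the slope. The documents do not support this. They give one common SD and no SD or correlation by visit. With equal residual SDs, Weeks 1-4 carry under half the weight; they dominate only if residual variance grows over time, which is plausible but not stated.

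One might also cite SAP 1.1, which rules out changes to the efficacy model. In context, that statement concerns changes after the primary analysis has been seen. It does not bar an amendment made beforehand.

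**Conclusion.** The plan fits one baseline slope to seven visits and tests one of them, and that slope is set mostly by visits before Week 12. If the slope changes over time, the Week 12 contrast is adjusted less efficiently: its SE is about 1-3% too large under moderate assumptions and 3-11% under steep ones. Chance imbalance is corrected imperfectly, by 0.01-0.02 log units for a one-SE imbalance under the moderate assumptions.

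A reader might go further and conclude that the primary result is biased or its error rate inflated. With complete data neither is so. Bias appeared only under the adverse dropout pattern; for slopes to -0.4 it was 0.010-0.023, or 3-7% of 0.33. Dropout related to baseline in the same way in both arms would largely cancel in the difference.

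All these sizes rest on assumed baseline SD, slopes and covariances. The case for the change is that its cost is small and bounded while the possible loss is larger, with up to 26% missing at Week 12 allowed for. It is a low-impact improvement and does not threaten the primary conclusion.

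**What to change.** Before unblinding for the primary analysis, add the baseline-by-visit interaction to the models in SAP 4.1.1 and 4.1.2, keeping baseline as a covariate. Sensitivity analyses 1 and 2, PCSK9 and the other lipids then inherit it, because they reuse these models. List it in SAP section 6 as a change from Protocol 9.4.2. While amending, state that the ANCOVA fallback is fitted at Week 12, so that its baseline adjustment matches.

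The cost is an SAP amendment, six more fixed-effect parameters and, if the slopes are truly equal, 1.0-1.3% more Week 12 variance (0.1-0.3 power points). No new data or participants are needed and the estimand is unchanged. After unblinding the same change would look data-driven, so the timing matters.
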